6.10. Maintenance of Randomization and Blinding

6.10.1. Maintenance of Randomization

Patient randomization codes will be maintained in a secure location at the service provider contracted to generate the codes. At the time of analysis (ie, after the efficacy portion of the study is completed), after receiving unblinding request from a Teva statistician, the service provider will provide the unblinded IMP assignment according to the processes defined in the relevant Standard Operating Procedure (SOP).

6.10.2. Blinding and Unblinding

Pharmacokinetic sample analysis by the bioanalytical laboratory may be performed during the course of the study. The population pharmacokinetic model for TV-44749 may be updated with new pharmacokinetic data emerging from the ongoing study. Population pharmacokinetic and pharmacokinetic analyses are required for the monitoring of the patients and enable IDMC evaluation of patient's safety-related issues. The process to ensure study integrity, maintenance of the double blind during Period 1, and the responsibilities of the relevant study personnel will be described in a pharmacokinetic analysis plan that will be approved prior to any data transfer, per the unblinded analyses group's interim analysis SOP and other relevant SOPs.

In addition, if a prioritized sample analysis is needed (ie, assessment of a pharmacokinetic sample for a potential PDSS event), relevant sponsor personnel may be unblinded during Period 1. Additional information will be provided in the separate predefined unblinded pharmacokinetic analyses plan.

As prolactin levels are highly affected by olanzapine and reach steady state approximately 8 weeks after treatment initiation ([Yang et al 2018](#)), in order to maintain the blind, prolactin level results obtained after first IMP administration and before visit 13 (8 weeks into Period 2) will not be available for review by the sponsor or the sites until Period 1 database lock. The IDMC will review the unblinded data periodically.

For information about personnel who may be aware of IMP assignments, see Section [6.9](#). These individuals will not be involved in the conduct of any study procedures or assessment of any adverse events.

In cases when knowledge of the IMP assignment is needed to make treatment decisions during Period 1, the investigator may unblind the patient's IMP assignment as deemed necessary, mainly in emergency situations. Individual randomization codes indicating the IMP assignment for each randomized patient will be available to the investigator(s) or pharmacist(s) at the investigational center via the RTSM, via internet. A back-up process will be available to the investigator in case of internet connection issues. Breaking of the treatment code can always be performed by the investigator without prior approval by the sponsor; however, the sponsor should be notified following the breaking of the treatment code during Period 1. The patient's IMP assignment should not be revealed to the sponsor (during Period 1).

If a blind is broken during Period 1, the patient will be withdrawn from the study, and the event will be recorded on the CRF. The circumstances leading to the breaking of the code should be fully documented in the investigator's study files and in the patient's source documentation. Assignment of IMP during Period 1 should not be recorded in any study documents or source document.

In blinded studies, for an adverse event defined as a suspected unexpected serious adverse reaction (SUSAR) (ie, reasonable possibility; see Section 8.1.4), the Global Patient Safety and Pharmacovigilance (GPSP) may independently request that the blind code be broken (on a case-by-case basis) to comply with regulatory requirements. The report will be provided in an unblinded manner for regulatory submission. If this occurs during Period 1, blinding will be maintained for the investigator and for other personnel involved in the conduct of the study and in the analysis and reporting of the data.

6.10.3. Independent Data Monitoring Committee

There will be an IDMC in this study. Details are given in [Appendix A](#).

6.11. Total Blood Volume

The total blood volume for routine sampling to be collected for each patient in this study is approximately 257 mL (at maximum), not including the optional samples for pharmacogenetics and biomarkers.

7. ASSESSMENT OF EFFICACY

For each assessment, where applicable, every effort should be made to retain the same rater for each patient throughout the course of the study.

7.1. Assessments of Efficacy

7.1.1. Positive and Negative Syndrome Scale

The PANSS is a 30-item scale used to evaluate positive and negative symptoms of schizophrenia (Kay et al 1987). The PANSS is used to identify the presence and severity of psychopathology symptoms, the relationship of these symptoms to one another, and the global psychopathology. Each item is scored on a 7-point scale ranging from 1 (absent) to 7 (extreme). The positive symptom scale includes 7 items with a maximum score of 49; the negative symptom scale includes 7 items with a maximum score of 49; and the general psychopathology scale includes 16 items with a maximum score of 112.

The PANSS will be administered by the investigator/trained rater at screening and all the time points specified in [Table 1](#) and [Table 2](#).

In addition to the patient and the rater, the information used for PANSS assessment may be obtained from 3rd party sources, such as the caregiver and an informant. In such cases, the name of the person/s who had provided the information and their relation to the patient (ie, caregiver or informant) should be recorded in the source documents.

7.1.2. Clinical Global Impression–Improvement

The CGI-I scale permits a global evaluation of the patient's overall improvement in symptoms. The CGI-I scale rates the patient's improvement relative to his or her symptoms on a 7-point scale ranging from 1 (very much improved) to 7 (very much worse) (Guy 1976b).

The CGI-I will be administered by the investigator/trained rater at time points specified in [Table 1](#) and [Table 2](#). The CGI-I during Periods 1 and 2 will be relative to the CGI-S score at the baseline visit (visit 2 in Period 1).

7.1.3. Clinical Global Impression–Severity of Illness Scale

The investigator/trained rater will complete the CGI-S at the time points specified in [Table 1](#) and [Table 2](#). The CGI-S allows the rater to assess the patient's current severity of illness on a scale of 1 to 7, where 1=normal/not at all ill, 2=borderline mentally ill, 3=mildly ill, 4=moderately ill, 5=markedly ill, 6=severely ill, and 7=among the most extremely ill patients (Guy 1976b).

7.1.4. Patient Global Impression-Improvement

The PGI-I scale is a 1-item patient-rated instrument that measures improvement of the patient's disease; the patient rates the perceived change in his/her condition in response to therapy (see time points specified in [Table 1](#) and [Table 2](#)).

The patient is instructed to select a response option on a scale of 1 to 7, where 1=very much better, 2=much better, 3=a little better, 4=no change, 5=a little worse, 6=much worse, 7=very much worse ([Steinert et al 2010](#)).

7.1.5. Personal and Social Performance Scale

The PSP will be administered to patients at the time points specified in [Table 1](#) and [Table 2](#) and is a clinician-rated instrument that measures personal and social functioning in patients with schizophrenia ([Morosini et al 2000](#)). The PSP is a 100-point single-item rating scale, divided into 10 equal intervals. The score is based on the assessment of patient's functioning in 4 categories: 1) socially useful activities, including work and study; 2) personal and social relationships; 3) self-care; and 4) disturbing and aggressive behaviors. Higher scores represent better personal and social functioning, with ratings from 91 to 100 indicating more than adequate functioning, while scores under 30 indicate functioning so poor that intensive supervision is required.

7.2. Other Assessment

7.2.1. Structured Clinical Interview for DSM-5, Clinical Trials Version (SCID-5-CT)

The SCID-5-CT is a semi-structured interview guide for making DSM-5 diagnoses. It will be administered at screening by a clinician or trained mental health professional who is familiar with the DSM-5 classification and diagnostic criteria.

The SCID-5-CT can be used to ensure that the major DSM-5 diagnoses are systematically evaluated and that all study patients have symptoms that meet the DSM-5 criteria for inclusion and exclusion, and to characterize a study population in terms of current and previous psychiatric diagnoses ([First et al 2015](#)).

7.2.2. Quality of Life Scales

The quality of life scales used in this study will include the 2 measures described below.

7.2.2.1. Schizophrenia Quality of Life Scale

The Schizophrenia Quality of Life Scale (SQLS) Revision 4 ([Martin and Allan 2007](#)) will be administered at the time points specified in [Table 1](#) and [Table 2](#) and will be used to capture quality of life. The 33-item measure yields 3 subscale scores: psychosocial, motivation/energy, and symptoms/side effects ([Wilkinson et al 2000](#)). Higher scores on the scales indicate worse quality of life.

7.2.2.2. [REDACTED]

[REDACTED]

[REDACTED]

[REDACTED]

8. ASSESSMENT OF SAFETY

In this study, safety will be assessed by qualified study personnel by evaluating reported adverse events (including serious adverse events, extrapyramidal symptoms, injection pain and other injection site findings [local tolerability]), vital signs (blood pressure, pulse and orthostatic changes, and temperature), body weight, laboratory tests, ECG, concomitant medication use, time to all-cause discontinuation, all-cause discontinuation rates and discontinuation rates due to adverse events (tolerability), and rating scales (including AIMS, BARS, SAS, C-SSRS, and CDSS).

Adverse events are categorized by ICH guidelines.

8.1. Adverse Events

8.1.1. Definition of an Adverse Event

An adverse event is any untoward medical occurrence in a patient or clinical investigation subject administered a pharmaceutical product and which does not necessarily have to have a causal relationship with this treatment.

An adverse event can, therefore, be any unfavorable and unintended physical sign, symptom, or laboratory parameter that develops or worsens in severity during the course of this study, or significant worsening of the disease under study, or of any concurrent disease, whether or not considered related to the IMP.

Accordingly, an adverse event can include any of the following:

- a new condition or the worsening of a pre-existing condition
- intercurrent illnesses
- physical injuries and the mechanism that caused the injury
- events possibly related to concomitant medication
- drug/drug interactions
- events occurring during diagnostic procedures or during any washout phase of this study
- laboratory or diagnostic test abnormalities

(Note: Abnormal laboratory or diagnostic test results at the screening visit that preclude a patient from entering the study or receiving study treatment are not considered adverse events.)

In Period 2, worsening of the schizophrenia will be assessed using PANSS, CGI-I, and CGI-S and should be recorded as an adverse event per investigator judgment.

A relapse event will be classified as an adverse event if specifically assessed as such by the investigator.

An adverse device effect is an adverse event related to the use of a medical device or a combination product. This includes adverse events resulting from insufficient or inadequate instructions for use, deployment, implantation, installation, operation, or any malfunction of the

medical device, including any event resulting from user error or from intentional misuse of the medical device. This definition includes events related to the procedures involved. For users or other persons, this definition is restricted to events related to medical devices.

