5.4. Withdrawal Criteria and Assessments/Procedures for the Patient

Patients are expected to participate in the study for its entire duration and perform the scheduled visits and procedures. Each patient is free to withdraw from the study or discontinue treatment with IMP at any time, without prejudice to their continued care, but every effort should be undertaken to determine the reason for discontinuation.

Patients must discontinue treatment with IMP and/or withdraw from the study if any of the following events occur:

1. Patient withdraws consent or requests discontinuation from the IMP and/or withdrawal from the study for any reason.
2. Patient develops an illness that would interfere with his/her continued participation.
3. Patient is noncompliant with the study procedures and assessments or administration of IMPs in the opinion of the investigator.
4. Patient takes prohibited concomitant medications as defined in this protocol (final decision to withdraw the patient will be on a case-by-case basis per sponsor discretion).
5. A female patient has a confirmation of pregnancy during the study from a positive pregnancy test.
6. The sponsor requests withdrawal of the patient.
7. Patient experiences an adverse event or other medical condition which indicates to the investigator that continued participation is not in the best interest of the patient.

Additionally, patients who meet the following study-specific criteria will be early terminated (ie, discontinued from further treatment with IMP and encouraged to complete the EOT and FU visits):

1. Patient is diagnosed with a clinically significant DSM-5 disorder other than schizophrenia.
2. A patient demonstrates a significant clinical deterioration that cannot be managed with permitted rescue medication as judged by the investigator based on any relevant history or observation made by the investigative site, and/ or requires other antipsychotic treatment apart from TV-44749. Hospitalization due to deterioration of schizophrenia that does not require other antipsychotic treatment will not be a withdrawal criterion unless determined as such by the investigator.
3. A patient experiences 3 events of pus-containing lesions (abscess, infection, or inflammation) at the site of injection requiring intervention/systemic treatment following 3 separate IMP injections.

Patients should be treated with standard of care after withdrawal from or termination of the study as appropriate.

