8.1.2. Recording and Reporting of Adverse Events

For recording of adverse event, the study period is defined for each patient as the time period from signature of the ICF to the end of the FU period. Treatment-emergent adverse events are defined as adverse events that occurred after the first dose of IMP was administered through the end of the study.

All adverse events that occur during the defined study period must be recorded both on the source documentation and the CRF, regardless of the severity of the event or judged relationship to the IMP. For serious adverse events and protocol-defined adverse events of special interest (PDAESIs) for expedited reporting to GPSP, the serious adverse event and PDAESI form must be completed, and the serious adverse event and the PDAESI must be reported immediately (Section 8.1.6.1). The investigator does not need to actively monitor patients for new adverse events after the end of the study.

At each contact with the patient, the investigator or designee must question the patient about adverse events by asking an open-ended question such as “Have you had any unusual symptoms or medical problems since the last visit? If yes, please describe.” All reported or observed signs and symptoms will be recorded individually, except when considered manifestations of a medical condition or disease state. A precise diagnosis will be recorded whenever possible. When such a diagnosis is made, all related signs, symptoms, and any test findings will be recorded collectively as a single diagnosis on the CRF and, if it is a serious adverse event or PDAESI for expedited reporting to GPSP, on the serious adverse event and PDAESI form.

The clinical course of each adverse event will be monitored at suitable intervals until resolved, stabilized, or returned to baseline; until the patient is referred for continued care to a health care professional; or until a determination of a cause unrelated to the IMP or study procedure is made.

The onset and end dates, duration (in case of adverse event duration of less than 24 hours), action taken regarding IMP, treatment administered, and outcome for each adverse event must be recorded both on the source documentation and the CRF.

The relationship of each adverse event to the IMP and the severity and seriousness of each adverse event, as judged by the investigator, must be recorded as described in Section 8.1.3, Section 8.1.4, and Section 8.1.5.

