8.1.5.1. Definition of a Serious Adverse Event

A serious adverse event is an adverse event occurring at any dose that results in any of the following outcomes or actions:

- results in death
- is a life-threatening adverse event (ie, the patient was at risk of death at the time of the event); it does not refer to an event which hypothetically might have caused death if it were more severe
- requires inpatient hospitalization or prolongation of existing hospitalization, which means that hospital inpatient admission or prolongation of hospital stay was required for treatment of an adverse event, or that they occurred as a consequence of the event

Hospitalizations scheduled before the patient signed the ICF will not be considered serious adverse events, unless there was worsening of the pre-existing condition during the patient's participation in this study.

- results in persistent or significant disability/incapacity (refers to a substantial disruption of one's ability to conduct normal life functions)
- is a congenital anomaly/birth defect
- an important medical event that may not result in death, be life-threatening, or require hospitalization but may jeopardize the patient and may require medical intervention to prevent one of the outcomes listed in this definition

Examples of such events are intensive treatment in an emergency room or at home for allergic bronchospasm, blood dyscrasias or convulsions that do not result in hospitalization, liver injury that meets the criteria for Hy's law, or the development of drug dependency or drug abuse. Note: Any suspected transmission of an infectious agent via a medicinal product is considered an important medical event.

All occurrences of possible drug-induced liver injury that meet Hy's law criteria, defined as **all** of the below, must be reported by the investigator to the sponsor as a serious adverse event:

- ALT or AST increase of $>3x$ the ULN
- total bilirubin increase of $>2x$ ULN
- absence of initial findings of cholestasis (ie, no substantial increase of alkaline phosphatase)

An adverse event that does not meet any of the criteria for seriousness listed above will be regarded as a nonserious adverse event.

A serious adverse device effect is an adverse device effect that results in any of the consequences characteristic of a serious adverse event and is reported per Section [8.1.6](#).

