5.8. Hospitalization and Re-hospitalization

Hospitalization/re-hospitalization data is collected during Period 1. Patients discharge status, discharge criteria, time duration (in days) of hospitalization from first IMP dose, and whether patients were re-hospitalized will be summarized using descriptive statistics. Hospitalization will include the full extent of its duration, i.e. if hospitalization continued to period 2 then the duration of hospitalization will include the time in period 2 as well.

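### Protocol 8.1.1 leaves it to the investigator whether a relapse is an adverse event, so a Period 2 admission for relapse can go unreported as serious and be unidentifiable in the readable outputs

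*Protocol*

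**What the plan says.** Protocol 8.1.1 opens broadly: "An adverse event is any untoward medical occurrence in a patient or clinical investigation subject administered a pharmaceutical product". Its account of what such an event can be ends with "or significant worsening of the disease under study, or of any concurrent disease, whether or not considered related to the IMP". Two narrower sentences follow. Worsening of schizophrenia in Period 2 is assessed on the PANSS, CGI-I and CGI-S and "should be recorded as an adverse event per investigator judgment". On relapse, the section says: "A relapse event will be classified as an adverse event if specifically assessed as such by the investigator".

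Protocol 8.1.2 sets the recording duty: "All adverse events that occur during the defined study period must be recorded both on the source documentation and the CRF", whatever the severity or judged relationship.

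Protocol 8.1.5.1 defines a serious adverse event as an adverse event with one of a list of outcomes. One of these is that it "requires inpatient hospitalization or prolongation of existing hospitalization", explained as admission needed to treat an adverse event or resulting from one.

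Protocol 5.4 foresees admission for relapse without loss of the patient from treatment: "Hospitalization due to deterioration of schizophrenia that does not require other antipsychotic treatment will not be a withdrawal criterion", unless the investigator decides otherwise. SAP 5.8 says "Hospitalization/re-hospitalization data is collected during Period 1" and mentions Period 2 only for a stay that runs on into it.

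**The concern.** Period 2 is the long-term safety phase. It is open-label and has no placebo group, and admission for psychiatric deterioration is a serious outcome that a reader would expect to find counted there. If the first step, calling the relapse an adverse event, is discretionary, then so is everything that depends on it: the 24-hour report to the sponsor (Protocol 8.1.6.1), the serious adverse event data available to the monitoring committee at its quarterly reviews (SAP 2.6.1), and the final tables.

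The people exercising the discretion can know the dose once the Period 2 assignment is revealed, and later the topline efficacy results (Protocol 6.9.4). Differences between doses, sites or regions in serious psychiatric events could then partly reflect labelling habits.

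**Working it through.** The plan states no figure on this point and no arithmetic applies. The check follows one case through the text: a patient in Period 2 on TV-44749 is newly admitted for relapse, is managed without another antipsychotic, stays on study drug, and the investigator does not assess the relapse as an adverse event.

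1. **Is the case foreseen?** Yes. Protocol 4.1 provides for hospitalization in Period 2 when an exacerbation is likely, and 5.4 provides for admission for deterioration with treatment continuing.
2. **Is it an adverse event?** Under the general definition and the recording duty it appears to be. Under the specific relapse sentence it is not, because the investigator has not assessed it as one. The specific sentence is the one a site would follow.
3. **Is it a serious adverse event?** Not on that reading. Section 8.1.5.1 applies only to adverse events. Its one stated hospitalization exception covers admissions scheduled before consent, and even that falls away if the pre-existing condition worsened during the study. Relapse is not exempted there; it drops out earlier, at 8.1.1.
4. **Does another readable output identify it?**

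| Output | What brings a patient in | Traced case |
|---|---|---|
| Adverse event and serious adverse event tables (SAP 8.4) | A recorded adverse event | Absent |
| Hospitalization and re-hospitalization (SAP 5.8) | Period 1 data, plus stays running on into Period 2 | A new Period 2 admission is not described |
| Disposition by reason (SAP 5.2) | Termination or discontinuation | Absent |
| Discontinuation rates and Kaplan-Meier curves (SAP 9.2) | Discontinuation | Absent as an event |
| By-visit tables (SAP 4.4) | Scheduled, end-of-treatment and follow-up visits; unscheduled visits are neither mapped nor shown | The unscheduled assessment is not shown |
| Period 2 PANSS and CGI-S (SAP 6.4) | Scheduled scores, summarized by group | Later scores enter the means, but no relapse or admission can be identified |

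No readable section defines relapse or plans a table of relapses or of Period 2 admissions. The gap is specific to Period 2: a Period 1 readmission would at least appear under SAP 5.8.

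**The case against.** The strongest case against has four parts.

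- **The drafting is permissive.** A reader might infer that 8.1.1 flatly contradicts itself. It does not quite do so. The sentence naming worsening of the disease says what an adverse event can be, the word significant already calls for judgment, and the Period 2 sentence can be read as an instruction to record. What remains is a tension with the unqualified opening definition and with the duty in 8.1.2.
- **Other text works against omission.** Adverse events are asked about at every contact, including the weekly calls. Suspected deterioration leads to an invitation to an unscheduled visit (Protocol Table 2, note cc). SAP Appendix B, in coding early terminations, names exacerbation of schizophrenia as an adverse event, so the plan expects at least some to be recorded. This makes omission less likely; it does not remove the discretion.
- **The case is narrow.** If another antipsychotic is needed, the patient is discontinued and appears in disposition by reason. If the investigator calls the relapse an adverse event, admission makes it serious. Both points stand. Concomitant drugs and dose adjustments are also recorded, but the planned summaries of them do not reveal an admission.
- **Some material is unseen.** The protocol-defined adverse events of special interest are redacted, although SAP 8.4 tabulates them. The exploratory endpoints are redacted too, and the Safety Monitoring Plan is not among the documents. Any of these might cover relapse. A relapse count under efficacy would still not place the event among the serious adverse events.

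A reader might also infer from SAP 5.8 that Period 2 admissions are not collected at all. The section describes Period 1 collection and is silent on new Period 2 admissions; it does not say they go unrecorded in source.

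**Conclusion.** The point holds as a reporting gap that should be closed. A discretionary sentence in 8.1.1 acts ahead of the seriousness criteria in 8.1.5.1, so a site can follow the stated rule and leave a hospital admission for relapse out of serious adverse event reporting. In the traced case no readable output identifies the admission as an event.

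The loss is possible rather than certain. It needs four things together: a new Period 2 admission for relapse, no other antipsychotic, treatment continued, and no adverse event assessment by the investigator.

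A reader might want to put a percentage on the understatement of the serious adverse event rate. The documents do not support one. They give no relapse admission rate, no share of such admissions left unclassified, and no count of patients entering Period 2. The 440 in Protocol 10.1 is a target for week 8 completers, and the 675 in the amendment details is patients randomized by 29 January 2024. Admissions already visible through discontinuation would also have to be removed.

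The conclusion assumes that neither the redacted list of adverse events of special interest nor the Safety Monitoring Plan already requires relapse admissions to be reported.

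**What to change.** 1. Reconcile Protocol 8.1.1 with 8.1.5.1: any worsening or relapse that meets a seriousness criterion, hospitalization included, is recorded as an adverse event and reported as serious. Keep investigator judgment for non-serious fluctuation in symptoms.
2. Extend the SAP 5.8 summary to new admissions in Period 2.
3. Apply the rule to Period 2 admissions already recorded in source, so that ascertainment is the same before and after the change.
4. If the Safety Monitoring Plan or the list of adverse events of special interest already says this, cross-refer to it in 8.1.1.

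These are reporting changes and leave patient management as it is. The cost is protocol and SAP wording, more serious adverse event forms, a limited re-check of source at sites with Period 2 patients, and a higher serious adverse event count. Without step 3, a change made while Period 2 is running would itself create a before-and-after difference in ascertainment.
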